13.2.3. Clinical Laboratory Evaluation Analyses

Descriptive statistics will be provided for selected clinical laboratory test results (hematology and blood chemistry) and changes from baseline by scheduled time of evaluation, including the End-of-Treatment Visit, maximum post-treatment value, and minimum post-treatment value.

Abnormal laboratory results will be graded according to NCI-CTCAE, v5.0, if applicable. A shift table, presenting the 2-way frequency tabulation for baseline and the worst post-treatment value according to the NCI-CTCAE grade, will be provided for selected clinical laboratory tests.

Abnormal clinical laboratory test results that are deemed of clinical significance or of grade 3 or 4 will be listed.

13.2.4. Vital Signs Analyses

Descriptive statistics will be provided for the vital signs measurements and changes from baseline by scheduled time of evaluation, including the End-of-Treatment Visit and the maximum and minimum post-treatment values.

13.3. Sample Size/Accrual Rate

The Dose Escalation phase of this study (Part 1) consists of 5 dose levels including at least 3 and up to 6 subjects for a minimum of 15 subjects if no DLT is reached, or a maximum of 30 subjects. An exploratory expansion phase including a goal of 10 subjects at the recommended phase 2 dose is also planned for a total in both phases of 25-40 subjects. During the dose-expansion phase, subjects removed from study after Cycle 1 based on the *TP53* mutation and/or deletion status will be replaced to ensure that a goal of 10 subjects with *TP53* wild-type status are enrolled in the dose-expansion cohort. Based on prior phase I and II studies at MDACC targeting a similar subject population, we estimate 1.5 subjects will be accrued every month, suggesting that 16-26 months will be needed to meet the sample size. Please note this assumes no interruption in accrual.

For the Dose Expansion phase (Part 2), the goal is to enroll 10 additional subjects. However, additional subjects may be enrolled if for example, two or more subjects are undergoing screening at the same time when only one study slot is remaining, and both subjects are deemed eligible for study participation. The maximum half width of the 95% confidence interval for the response rate will be 32% for 10 subjects. Including the 6 subjects enrolled at the MTD in the Part I (dose-escalation phase), the maximum half width of the 95% confidence interval for 16 subjects will be 25%.

Estimated monthly accrual is 2.5 subjects/month.

PLANNED ENROLLMENT REPORT

Racial Categories	Ethnic Categories				Total
	Not Hispanic or Latino		Hispanic or Latino		
	Female	Male	Female	Male	
American Indian/ Alaska Native	0	1			1
Asian	1	1			2
Native Hawaiian or Other Pacific Islander	1	0			1
Black or African American	3	3			6
White	12	12			24
More Than One Race			3	3	6

Racial Categories	Ethnic Categories				Total
	Not Hispanic or Latino		Hispanic or Latino		
	Female	Male	Female	Male	
Total	17	17	3	3	40

PHS 398 / PHS 2590 (Rev. 08/12 Approved Through 8/31/2015)

OMB No. 0925-0001/0002

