
of the trial. To determine the MTD, escalation for KRT-232 (AMG 232) will be conducted following the “3+3” design with de-escalation. A cohort of three subjects will be treated at the starting dose level and observed until the end of the first cycle (subjects non-evaluable for DLT will be replaced). The dose level will be escalated with each new cohort until at least one out of three subjects of a cohort experiences DLT. If one subject experiences a DLT, then three additional subjects will be treated at the same dose level; if none of the three additional subjects experiences a DLT, then the dose escalation will be continued by treating the next cohort of three subjects at the next higher dose level. If at least two out of up to six subjects at a dose level experience a DLT, the MTD will be considered to have been exceeded, and up to 3 more subjects will be treated at the next lower dose if there are less than 6 subjects already treated at that dose. The dose steps for escalation are displayed below:

Dose-Escalation Schedule	
Dose Level	KRT-232 (AMG 232) Dose
- 1	30 mg/day PO x 7 days out of 28 day cycle
+ 1	60 mg/day PO x 7 days out of 28 day cycle
+ 2	90 mg/day PO x 7 days out of 28 day cycle
+ 3	120 mg/day PO x 7 days out of 28 day cycle
+ 4	180 mg/day PO x 7 days out of 28 day cycle
+ 5	240 mg/day PO x 7 days out of 28 day cycle

If dose-de-escalation is needed for Dose level 1, Dose level -1 is defined as 30 mg/day x 7 days out of 28 day cycle.

Part B (Dose-expansion scheme)

After determination of the KRT-232 (AMG 232) MTD or proven tolerability of the highest planned dose, a goal of 10 additional subjects will be treated in the Part 2 dose expansion in combination with KRd. The tentative RP2D will be determined based on the review of safety data at the MTD. The primary objective of this dose-expansion phase is to confirm the safety and tolerability of KRT-232 (AMG 232) + KRd at the MTD and tentative RP2D in a goal of 10 subjects with relapsed and/or refractory multiple myeloma.

Dose-Limiting Toxicity (DLT) Definition

A DLT is defined as any treatment emergent adverse event (TEAE) during the first treatment cycle that does not have a clear alternative cause (e.g., disease under study, concomitant therapy) based on the following criteria using NCI-CTCAE v5.0:

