Sample Size:	
The Dose Escalation phase of this study (Part 1) consists of 5 dose levels including at least 3 and up to 6 subjects for a minimum of 15 subjects if no DLT is reached, or a maximum of 30 subjects. An exploratory expansion phase with a goal enrollment of 10 subjects at the recommended phase 2 dose is also planned for a total in both phases of 25-40 subjects. During the dose-expansion phase, subjects removed from study after Cycle 1 based on the TP53 mutation and/or deletion status will be replaced to ensure that a goal of 10 subjects with TP53 wild-type status are enrolled in the dose-expansion cohort. Based on prior phase I and II studies at MDACC targeting a similar subject population, we estimate 1.5 subjects will be accrued every month, suggesting that 16-26 months will be needed to meet the sample size. Please note this assumes no interruption in accrual.
 
For the Dose Expansion phase (Part 2), a goal of 10 additional subjects will be enrolled. The maximum half width of the 95% confidence interval for the response rate will be 32% for 10 subjects. Including the 6 subjects enrolled at the MTD in the Part I (dose-escalation phase), the maximum half width of the 95% confidence interval for 16 subjects will be 25%.

Statistical Considerations:	
The primary analysis is to assess the safety and tolerability of KRT-232 (AMG 232) + KRd in subjects with relapsed and/or refractory myeloma and to determine the MTD/tentative RP2D of KRT-232 (AMG 232) + KRd.
 
All subjects who receive any amount of the study drug will be evaluable for toxicity. The DLT-evaluable period will be during cycle 1, although toxicity will be monitored throughout the course of treatment. The primary analysis will occur after all subjects in Part B have either discontinued the study or completed at least 6 months of treatment.

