5.4. KRT-232 (AMG 232) + Carfilzomib, Lenalidomide, and Dexamethasone Treatment Plan

Dose Regimen

KRT-232 (AMG 232) + carfilzomib, lenalidomide, and dexamethasone will be administered per the following schedule:

Cycles 1-12 (28 day cycle)

- KRT-232 (AMG 232) once daily by mouth 7 out of 28 days
- Carfilzomib 20 mg/m² IV on Days 1 and 2 of Cycle 1, escalating to 27 mg/m² IV on Days 8, 9, 15, 16 of Cycle 1 and continuing on Days 1, 2, 8, 9, 15, 16 of Cycles 2 through Cycle 12
- Lenalidomide 25 mg PO on Days 1-21
- Dexamethasone 40 mg PO or IV on Days 1, 8, 15, and 22

Cycles 13-18 (28 days each)

- KRT-232 (AMG 232) once daily by mouth 7 out of 28 days
- Carfilzomib 27 mg/m² IV on Days 1, 2, 15, and 16
- Lenalidomide 25 mg PO on Days 1-21
- Dexamethasone 40 mg PO or IV on Days 1, 8, 15, and 22

Cycles 19+ (28 days each)

- KRT-232 (AMG 232) once daily by mouth 7 out of 28 days
- Lenalidomide 25 mg PO on Days 1-21
- Dexamethasone 40 mg PO or IV on Days 1, 8, 15, and 22

Part A (Dose-escalation scheme)

The MTD is defined as the highest dose at which six subjects have been treated and less than two subjects experienced DLT within the first cycle of treatment in Phase I of the trial. To determine the MTD, escalation for KRT-232 (AMG 232) will be conducted following the “3+3” design with de-escalation. A cohort of three subjects will be treated at the starting dose level and observed until the end of the first cycle (subjects non-evaluable for DLT will be replaced). The dose level will be escalated with each new cohort until at least one out of three subjects of a cohort experiences DLT. If one subject experiences a DLT, then three additional subjects will be treated at the same dose level; if none of the three additional subjects experiences a DLT, then the dose escalation will be continued by treating the next cohort of three subjects at the next higher dose level. If at least two out of up to six subjects at a dose level experience a DLT, the MTD will be considered to have been exceeded, and up to 3 more subjects will be treated at the next lower dose if there are less than 6 subjects already treated at that dose. The dose steps for escalation are displayed below:

Dose Escalation Schedule	
Dose Level	Dose of KRT-232 (AMG 232)*
- 1	30 mg/day PO x 7 days out of 28 day cycle
+ 1	60 mg/day PO x 7 days out of 28 day cycle
+ 2	90 mg/day PO x 7 days out of 28 day cycle
+ 3	120 mg/day PO x 7 days out of 28 day cycle

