+ 4	180 mg/day PO x 7 days out of 28 day cycle
+ 5	240 mg/day PO x 7 days out of 28 day cycle

If dose-de-escalation is needed for Dose level 1, Dose level -1 is defined as 30 mg/day x 7 days out of 28 day cycle.

There should be no dose modifications of KRT-232 (AMG 232) and KRd during the DLT-evaluable period (Cycle 1). Subjects requiring dose-reductions during the DLT-evaluable period will be considered a DLT.

Part B (Dose-expansion scheme)

After determination of the KRT-232 (AMG 232) MTD or proven tolerability of the highest planned dose, and a goal of 10 additional subjects will be treated in the Part 2 dose expansion in combination with KRd. The primary objective of this dose-expansion phase is to confirm the safety and tolerability of KRT-232 (AMG 232) + KRd at the MTD and tentative RP2D in a goal

of 10 subjects with relapsed and/or refractory multiple myeloma. The tentative RP2D will be determined based on the review of safety data at the MTD.

During the dose-expansion phase, subjects removed from study after Cycle 1 based on the *TP53* mutation and/or deletion status will be replaced to ensure that a goal of 10 subjects with *TP53* wild-type status are enrolled in the dose-expansion cohort.

The subject will be requested to maintain a medication diary of each dose of medication. The medication diary will be returned to clinic staff at the end of each course.

KRT-232 (AMG 232)

The following medications and/or therapies should not be administered within the timeframes specified prior to enrollment and during the study (unless otherwise specified below):

- Antitumor therapy (chemotherapy, antibody therapy, molecular targeted therapy, retinoid therapy, hormonal therapy, or investigational agent) within 21 days of study day 1; concurrent use of hormone deprivation therapy for hormone-refractory prostate cancer or breast cancer and continuation of previous hormone therapy in breast cancer subjects are permitted.
- Treatment with immune modulators including, but not limited to, corticosteroids, cyclosporine and tacrolimus within 3 weeks prior to enrollment, except for a corticosteroid dose equivalent to dexamethasone of ≤ 4 mg/day
- Therapeutic or palliative radiation therapy within 4 weeks of KRT-232 (AMG 232) day 1.

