5.6. Definition of Dose-Limiting Toxicity

A DLT is defined as any treatment emergent adverse event (TEAE) during the first treatment cycle that does not have a clear alternative cause (e.g., disease under study, concomitant therapy) based on the following criteria using NCI-CTCAE v5.0:

- Hematological toxicity
 - Grade 3 or 4 neutropenia with fever $\geq 38^0$ C lasting > 48 hours
 - Grade 4 neutropenia lasting > 7 days
 - Grade 3 or 4 thrombocytopenia associated with $>$ grade 1 bleeding. Grade 4 thrombocytopenia that persists for > 14 days, despite holding treatment
 - Grade 4 anemia, unexplained by underlying disease
 - Any other grade 4 hematologic toxicity that does not resolve to subject's pre-treatment baseline level within 72 hours
- Non-hematological toxicity
 - Grade ≥ 3 nausea, vomiting or diarrhea lasting longer than 72 hours despite optimal medical support
 - Grade ≥ 3 non-hematological toxicity (excluding increased serum creatinine, or electrolyte abnormalities that are not clinically significant and require no treatment)
 - Any grade 3 electrolyte abnormalities that do not resolve to grade ≤ 2 within 72 hours
 - Grade 3 fatigue persisting > 7 days
 - Grade ≥ 3 acute kidney injury (creatinine $> 3 \times$ baseline or > 4.0 mg/dL) lasting > 72 hours
 - Any other grade 3 or 4 non-hematologic toxicities not predefined above will be considered a DLT.
 - A delay of ≥ 14 days in commencing Cycle 2 Day 1 due to lack of adequate

recovery of KRT-232 (AMG 232) +KRD-related toxicities will be considered a DLT.

Subjects who receive < 75% of the planned study drug doses during the first cycle of (i.e. $\leq 5/7$ daily doses of KRT-232 (AMG 232) will be considered non-evaluable for purposes of determining the MTD (unless due to a DLT) and will be replaced. Subjects who experience a DLT during the DLT-evaluable period will be considered evaluable for the purposes of determining the MTD as per Section 13.1.4

Management and dose modifications associated with the above adverse events are outlined in Section 6.

Dose escalation will proceed within each cohort according to the following scheme. Dose-limiting toxicity (DLT) is defined above.

Number of Subjects with DLT at a Given Dose Level	Escalation Decision Rule
0 out of 3	Enter 3 subjects at the next dose level.

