≥ 2	Dose escalation will be stopped. This dose level will be declared the maximally administered dose (highest dose administered). Three (3) additional subjects will be entered at the next lowest dose level if only 3 subjects were treated previously at that dose.
1 out of 3	Enter at least 3 more subjects at this dose level. If 0 of these 3 subjects experience DLT, proceed to the next dose level. If 1 or more of this group suffer DLT, then dose escalation is stopped, and this dose is declared the maximally administered dose. Three (3) additional subjects will be entered at the next lowest dose level if only 3 subjects were treated previously at that dose.
≤ 1 out of 6 at highest dose level below the maximally administered dose	This is generally the recommended phase 2 dose. At least 6 subjects must be entered at the recommended phase 2 dose.

5.7. Dose Expansion Cohorts:

Once the RP2D is reached, a goal of 10 additional subjects will be treated at this dose. For the expansion cohort, subjects will continue to be monitored for occurrence of DLT. If 2 of the first 5 subjects or if ≥ 4 of 10 subjects experience DLT, the Principal Investigator will discuss with all study investigators and with CTEP whether further addition of subjects is needed to re-assess the RP2D. When the first 5 additional patients are enrolled in the expansion phase, with a total of 11 patients including the 6 patients who had been already treated at the RP2D, the probabilities of observing 3 or more patients with DLT are 22.1%, 68.7% and 96.7% if the true toxicity rate are 15%, 30%, and 50%. When all 10 additional patients are enrolled in the expansion phase, with a

total of 16 patients including the 6 patients who had been already treated at the RP2D, the probabilities of observing 5 or more patients with DLT are 7.9%, 55%, and 96.2% if the true toxicity rate are 15%, 30%, and 50%. Monitoring of all safety and toxicity data is done by the Principal Investigator and the Corresponding Organization on a real-time basis as data are entered into Medidata Rave using the Web Reporting Module. All participating sites are expected to notify the Principal Investigator when a DLT has occurred.

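### The no-DLT minimum (15 in Part A, 25 in total) puts three subjects at the top dose, while the MTD definition, decision table, 5.7 probabilities and 16-subject interval count six; 13.3 also gives two accrual rates

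*Combined protocol and SAP*

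**What the plan says.** Section 13.3 and the synopsis (Sample Size) give Part A five dose levels, "including at least 3 and up to 6 subjects for a minimum of 15 subjects if no DLT is reached", and a maximum of 30. Ten expansion subjects bring the total to 25–40.

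Other parts of the document bear on how many subjects the top level receives:

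- **Decision table (5.6), after 0 of 3 with a DLT:** "Enter 3 subjects at the next dose level".
- **Decision table, last row:** at least six subjects are required at the recommended phase 2 dose. The row concerns the highest level below the maximally administered dose.
- **Section 5.4, Part A (also in the synopsis):** "The MTD is defined as the highest dose at which six subjects have been treated", with fewer than two DLTs.
- **Section 5.4, Part B:** the expansion opens "After determination of the KRT-232 (AMG 232) MTD or proven tolerability of the highest planned dose". The synopsis has the same alternative. Neither place attaches a number of subjects to it.
- **Section 5.7:** DLT probabilities are given first "with a total of 11 patients including the 6 patients who had been already treated at the RP2D", then for a "total of 16 patients including the 6 patients who had been already treated at the RP2D".
- **Section 13.3, precision:** the 25% half-width is for 16 subjects, six of them from Part A at the MTD.

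Section 13.3 first estimates 1.5 subjects per month, hence 16–26 months, and later gives 2.5 per month. The synopsis gives only 1.5. Section 13.7 applies 75% consent to 25–40 subjects and expects 19–30 optional biopsies.

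**The concern.** The minimum is stated for one specific path, the one without any DLT. On that path escalation runs through all five levels and ends with 0 of 3 at the highest. The table's instruction then points to a level that does not exist. The other ways of adding three subjects to a level (one DLT among the first three there, or a higher level being exceeded) cannot occur. A count of 15 therefore means three subjects at the dose that goes into Part B, where the rest of the plan assumes six.

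At stake is how many Part A subjects support the dose taken forward, which bears on the primary objective. The lower ends of the sample size, duration and biopsy ranges depend on the same count, and so does whether the printed pooled precision and DLT probabilities apply on this path. The two accrual rates imply durations that differ by about 7 to 11 months.

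**Working it through.** **Inputs.** Five levels, three to six per level, and ten in Part B (13.3); six at the MTD (5.4); six carried over in 5.7 and in the 13.3 interval; 75% biopsy consent (13.7); 1.5 and 2.5 subjects per month (13.3).

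**1. The plan's own totals reproduce.**
- Minimum: 5 × 3 = 15, and 15 + 10 = 25.
- Maximum: 5 × 6 = 30, and 30 + 10 = 40.
- Biopsies: 0.75 × 25 = 18.75 (printed as 19) and 0.75 × 40 = 30.

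**2. The 5.7 probabilities reproduce with six carried over, and not with three.** Exact binomial tails at true DLT rates of 15%, 30% and 50%:

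| Event | 15% | 30% | 50% |
|---|---|---|---|
| ≥3 of 11 (6 + 5), as printed | 22.1% | 68.7% | 96.7% |
| ≥5 of 16 (6 + 10), as printed | 7.9% | 55.0% | 96.2% |
| ≥3 of 8 (3 + 5) | 10.5% | 44.8% | 85.6% |
| ≥5 of 13 (3 + 10) | 3.4% | 34.6% | 86.7% |

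**3. The half-widths reproduce.** The maximum is z × √(0.25/n).
- n = 10: 31.0% with z = 1.96, 31.6% with z = 2, 31.3% exact; printed 32%.
- n = 16: 24.5%, 25.0% and 25.3% respectively; printed 25%.

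Each printed figure is right on its own inputs. The conflict is between them.

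**4. If six are treated at the top level on the no-DLT path.**
- Part A: 4 × 3 + 6 = 18. Total: 18 + 10 = 28.
- Biopsies: 0.75 × 28 = 21.

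**5. If three are treated there.**
- Pooled set: 3 + 10 = 13.
- Maximum half-width: 1.96 × √(0.25/13) = 27.2% (exact 27.8%).

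**6. Neither 25 nor 28 is a floor for the trial.** Take 0 of 3 at level 1, two DLTs among three at level 2, then three more at level 1. Part A has 3 + 3 + 3 = 9 subjects. With Part B the total is 19, and 0.75 × 19 = 14.25 biopsies.

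**7. Accrual (separate).**
- At 1.5 per month: 25/1.5 = 16.7 and 40/1.5 = 26.7 months, which is the stated 16–26 truncated.
- At 2.5 per month: 25/2.5 = 10 and 40/2.5 = 16 months.
- With 28 as the no-DLT total, the lower end is 28/1.5 = 18.7 or 28/2.5 = 11.2 months.

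**8. The 5.7 trigger (separate).** The trigger is two of the first five expansion subjects, read here as at least two, or four or more of ten. It uses expansion subjects only. P(either) = P(X₅ ≥ 2) + Σ P(X₅ = x) × P(Y₅ ≥ 4 − x) over x = 0, 1, where X₅ and Y₅ are the DLT counts in the first and second five. At a 30% rate this is 0.472 + 0.168 × 0.031 + 0.360 × 0.163 = 0.536.

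| Trigger | 15% | 30% | 50% |
|---|---|---|---|
| ≥2 of first 5 | 16.5% | 47.2% | 81.3% |
| ≥4 of 10 | 5.0% | 35.0% | 82.8% |
| Either look | 17.6% | 53.6% | 89.6% |

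**The case against.** The strongest reply is that the plan already answers the question. A reader might infer that nothing in it calls for six subjects at the top dose, but the documents do not support that. The last row of the decision table requires at least six at the recommended phase 2 dose. Together with the MTD definition and the 13.3 precision statement, it points to six. On this view 15/25 is simply a count that was not brought into line. Most of that stands, and it is why six is the better-supported reading. It does not close the matter. The row is written for a level below the maximally administered dose, and its requirement could be met by counting Part B subjects. The route through "proven tolerability of the highest planned dose" has no number. The step after 0 of 3 at the last level is not described.

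A reader might also take 28 subjects and 21 biopsies as new lower bounds. They are not, because early de-escalation gives fewer (step 6).

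The 16-subject half-width is explicitly conditional on six at the MTD, so it is correct as stated. It concerns a response rate that is secondary in Part B and exploratory in Part A.

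The trigger probabilities do not follow from 15 versus 18, because the trigger counts expansion subjects only and works the same either way. It also leads to a discussion with CTEP and the study investigators, not to an automatic stop.

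The two accrual rates may have different bases: the 1.5 is attributed to earlier studies at the lead centre, and other sites take part. The text does not say so.

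**Conclusion.** The inconsistency is real and minor. On the no-DLT path, 15 and 25 imply three subjects at the top dose, against six in the MTD definition, the decision table, the 5.7 probabilities and the 13.3 interval. Section 13.3 therefore disagrees with itself.

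If six stands, the no-DLT figures rise by three, and the biopsy expectation goes from 19 to 21. If three is allowed, the maximum half-width goes from 25% to about 27%, and the printed 11- and 16-patient probabilities do not apply on that path. The maximum of 30/40, the enrolment table total of 40 and the working of the 5.7 trigger are unaffected.

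The accrual conflict and the missing trigger probabilities are separate points. No analysis depends on the accrual rate. The printed pooled figures should not be read as the trigger's chance of firing: at a true rate of 30% that chance is 47.2% at the first look and 53.6% over both, beside printed values of 68.7% and 55%.

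These results assume exactly ten expansion subjects, independent DLTs at a common rate, and at least two for the first-look trigger.

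**What to change.** - **Number at the dose taken to Part B.** Reconcile the synopsis, 5.4 (Parts A and B), the 5.6 decision table, 5.7 and 13.3 on how many Part A subjects are treated at that dose. Cover the case of 0 of 3 at the highest level and the tolerability route into Part B.
- **If six stands:** restate the no-DLT figures as 18 in Part A and 28 in total (13.3 and synopsis), and the matching biopsy expectation in 13.7 as 21. Label these as values for the no-DLT path, since early de-escalation can give fewer.
- **If three is allowed:** say that the pooled set on that path is 13 with a maximum half-width of about 27%, and that the printed 11- and 16-patient probabilities do not apply there.
- **Accrual:** keep one rate in 13.3 and the synopsis, and make the stated duration agree with it.
- **Section 5.7:** print the trigger's own probabilities (either look: 17.6%, 53.6% and 89.6% at true rates of 15%, 30% and 50%), and state whether the first look means at least two.

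The cost is protocol wording. The maximum enrolment does not change. Either the no-DLT minimum rises by three, or the precision and probability statements are qualified for that path.
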